5.4.3 Reporting Requirements for Pregnancies

5.4.3.1 Pregnancies in Female Patients

Female patients of childbearing potential will be instructed to immediately inform the investigator if they become pregnant during the study or 90 days after the last dose of study drug. A Pregnancy Report eCRF should be completed by the investigator within 24 hours after learning of the pregnancy and submitted via the EDC system. A

pregnancy report will automatically be generated and sent to Roche Safety Risk Management. Pregnancy should not be recorded on the Adverse Event eCRF. The investigator should discontinue study drug and counsel the patient, discussing the risks of the pregnancy and the possible effects on the fetus. Monitoring of the patient should continue until conclusion of the pregnancy.

In the event that the EDC system is unavailable, a Pregnancy Report worksheet and Pregnancy Fax Coversheet should be completed and faxed to Roche Safety Risk Management or its designee within 24 hours after learning of the pregnancy, using the fax numbers provided to investigators (see “Protocol Administrative and Contact Information & List of Investigators”).

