3.1.4 Extended Follow-Up

At the common closeout date, patients whose *peripheral* B cells remain depleted will continue to attend study visits every 3 months until their *peripheral* B-cell counts have returned to *pre-rituximab* baseline levels or to within the normal range for the population, whichever is lower. *Safety (adverse events), central laboratory and immunological parameters, including immunoglobulin, will continue to be assessed in extended safety follow-up (see [Appendix 1](#)).*

If a patient receives any B cell-depleting therapy (*commercial or investigational*) or any other agent that affects the return of B cells including, but not limited to, rituximab, CYC, and AZA, on or after the common closeout date, he or she will not be followed any further (although routine clinical follow up after the end of the study will continue, according to local practice).

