3.1.8 Early Study Drug Withdrawal

The investigator may also withdraw a participant from study treatment if he or she judges that continuing on rituximab is no longer in the participant's best interest. These participants will remain in the study *for follow-up*, but will be asked to complete a withdrawal visit (see [Appendix 1](#)). *From the point of withdrawal, a patient may no longer receive rituximab as part of this protocol.* They will continue to be followed until the common closeout date. At the common closeout date, patients whose *peripheral B* cells remain depleted, will continue to attend study visits every 3 months until their

peripheral B-cell counts have returned to *pre-rituximab* baseline level or to within the normal range for the population, whichever is lower (see Section 3.1.4).

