3.2 END OF STUDY

Follow up of all participants will continue until the common closeout date, when the final participant enrolled has completed his or her Month 18 study visit.

At the time of the common closeout date for each patient, the scheduled study visit occurring before or at the common closeout date will represent the end of main study visit. However, all participants with *peripheral* B-cell counts below the LLN or *pre-rituximab* baseline value will enter extended follow up, as described in Section 3.1.4. If the trial is stopped early, all participants will be withdrawn from the study at the time of the termination of the study.

The end of the study will occur when the last participating patient completes the final scheduled visit (inclusive of extended follow up) or when the Sponsor decides to discontinue the study or development program.

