4.3.4 Retreatment with Rituximab

After Month 6, if patients require retreatment with rituximab, further courses will be provided by the Sponsor until the common closeout date. The dose of rituximab and the frequency of retreatment for the maintenance of remission will be at the discretion of the investigator.

Following administration of the first infusion the investigator should review the following safety criteria before administering subsequent infusions of rituximab.

The following are absolute contraindications to receipt of further infusions of rituximab in this study:

- An infusion reaction which necessitated complete discontinuation of the study infusions
- Significant deterioration in patient's general health status since inclusion into the study that results in the patient meeting the exclusion criteria related to General Health
- Emergent primary or secondary immunodeficiency recognized during the study period, including new HIV infection, de novo hepatitis B, hepatitis C, or active tuberculosis infection

Patients who have any of the absolute contraindications to receipt of study infusions with rituximab will be withdrawn from the study and should be encouraged to enter Follow Up.

Patients who develop malignancy during the study will not be able to receive further courses of treatment with the study medication. However, patients with basal cell carcinoma, squamous cell carcinoma of the skin or melanoma in situ (Clarke's Level I), or cervical carcinoma in situ with no stromal invasion (stage 0), which have been completely excised and can be considered as cured, may be retreated with study medication at the discretion of the investigator.

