5.2.3.9 Pregnancy

IgGs are known to cross the placental barrier.

Developmental toxicity studies performed in cynomolgus monkeys revealed no evidence of embryotoxicity in utero. Newborn offspring of maternal animals exposed to rituximab were noted to have depleted B-cell populations during the postnatal phase.

B-cell levels in human neonates following maternal exposure to rituximab have not been studied in clinical trials. There are no adequate and well-controlled data from studies in pregnant females; however, transient B-cell depletion and lymphocytopenia have been reported in some infants born to mothers exposed to rituximab during pregnancy. For these reasons, rituximab should not be administered to pregnant females unless the possible benefit outweighs the potential risk.

Female patients in Tanner stages ≥ 2 (see [Appendix 4](#)) or post-onset of menarche should employ effective contraceptive methods during and for up to 12 months after treatment with rituximab.

Additional information about rituximab is given in the Investigator's Brochure.

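### A female patient who leaves the study within 12 months of her last rituximab dose may not be asked to report a pregnancy for up to 275 days of the protocol's own contraception period

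*Protocol*

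**What the plan says.** **Notification.** Protocol 5.4.3.1 tells female patients of childbearing potential to "inform the investigator if they become pregnant during the study or 90 days after the last dose of study drug". I read the bare *or* as whichever is later. The same section has the investigator keep monitoring until the pregnancy ends, and it keeps pregnancy off the adverse event form.

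**Contraception.** Under Protocol 5.2.3.9, female patients at Tanner stage 2 or above, or past menarche, "should employ effective contraceptive methods during and for up to 12 months after treatment with rituximab".

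**Investigator reporting.** Section 5.4 lists pregnancies among the events that go to the sponsor within 24 hours of the investigator learning of them. It sets no end date.

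**After the study.** Section 5.6 covers deaths, serious events and other events of concern believed related to treatment, together with cancer and birth defects in later offspring. A pregnancy as such is not listed. Sections 5.4.3.3 and 5.4.3.4 class spontaneous abortions and birth defects as serious adverse events.

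**Who stays in.** Of patients withdrawn from study drug only, 3.1.8 says: "They will continue to be followed until the common closeout date". At closeout, a patient whose peripheral B-cell count is below the lower limit of normal or her pre-rituximab "baseline value will enter extended follow up, as described in Section 3.1.4" (3.2). Visits then run until counts are back to pre-rituximab "baseline levels or to within the normal range for the population, whichever is lower" (3.1.4).

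**Who can leave.** Parents may withdraw a child at any time, and patients may be lost to follow-up (4.6.1). The investigator or sponsor may withdraw a patient (3.1.7, 4.6.2). Section 4.3.4 withdraws patients with an absolute contraindication to further infusions, and only encourages follow-up. On early termination, 3.2 states: "If the trial is stopped early, all participants will be withdrawn from the study at the time of the termination of the study". Retreatment is possible late: after Month 6, "further courses will be provided by the Sponsor until the common closeout date" (4.3.4). Extended follow-up ends if the patient receives an agent that affects B-cell return, including "rituximab, CYC, and AZA, on or after the common closeout date, he or she will not be followed any further" (3.1.4).

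**The concern.** For up to a year after the last dose the protocol treats conception as something to avoid. Yet a patient who has left the study is asked to mention a pregnancy only in the first 90 days after that dose. From then to the end of the contraception period, a pregnancy reaches the safety database only if the investigator happens to hear of it or if it leads to an event reportable under 5.6.

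Section 5.2.3.9 itself explains why this information has value. B-cell levels in newborns after maternal exposure have not been studied in clinical trials, and temporary B-cell loss and low lymphocyte counts have been seen in some exposed infants. If adverse outcomes are reported but the pregnancies behind them are not, there is no denominator. A transient finding in an infant may also pass unnoticed if nobody knows of the exposure. The trial enrols adolescents, so the question is a practical one.

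**Working it through.** The documents give no figure to reproduce, so the check is date arithmetic.

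**Inputs**
- Notification limit: 90 days after the last dose (5.4.3.1)
- Contraception period: up to 12 months (5.2.3.9), taken as 365 days. This is a ceiling.
- Fourth induction infusion: Day 22. Month 18: Day 545 (Appendix 1).
- Closeout for the last patient enrolled: her Month 18 visit (3.2), Day 545

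**General formula.** Let L be the days from last dose to study exit. Days in the contraception period without an instruction to notify:

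gap = max(0, 365 - max(90, L))

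| L (days) | Gap (days) |
|---|---|
| 0 to 90 | 365 - 90 = 275 |
| 180 | 365 - 180 = 185 |
| 270 | 365 - 270 = 95 |
| 364 | 365 - 364 = 1 |
| 365 or more | 0 |

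The maximum is 270 days if 12 months is counted as 360 days, and 276 if counted as 366.

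**Induction course only.** The contraception period ends on Day 22 + 365 = 387. The 90 days end on Day 22 + 90 = 112. So gap = max(0, 387 - max(exit day, 112)).

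| Exit | Gap (days) |
|---|---|
| Month 1 (Day 29) | 387 - 112 = 275 |
| Month 2 (Day 60) | 387 - 112 = 275 |
| Month 4 (Day 120) | 387 - 120 = 267 |
| Month 6 (Day 180) | 387 - 180 = 207 |
| Month 9 (Day 270) | 387 - 270 = 117 |
| Month 12 (Day 365) | 387 - 365 = 22 |
| Month 15 (Day 455) or later | 0 |

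A patient who completes Month 18 has 545 - 22 = 523 days in the study after her last dose. With the Appendix 2 visit windows at their least favourable this is (545 - 10) - (22 + 3) = 510. Both exceed 365, so she has no gap.

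**Late retreatment.** For the last-enrolled patient, with last dose on Day d and *no* extended follow-up, gap = max(0, d + 365 - max(545, d + 90)).

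| Last dose | Gap (days) |
|---|---|
| Day 270 | 635 - 545 = 90 |
| Day 365 | 730 - 545 = 185 |
| Day 455 | 820 - 545 = 275 |
| Day 545 | 910 - 635 = 275 |

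These are worst cases. Time spent in extended follow-up counts as time in the study and has urine pregnancy tests scheduled (Appendix 1). Each day spent there beyond the date notification would otherwise end removes one day of gap. The gap is zero once the patient reaches 12 months after the dose.

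**The case against.** The strongest reply is that the reporting system does not stop at 90 days. Section 5.4 obliges the investigator to report any pregnancy learned of, whatever its relation to treatment and with no end date. A reader might infer from the two windows that a pregnancy after day 90 need not be reported at all. The documents do not support that, because only the patient's instruction is limited. This part of the reply stands and fixes the scope of the point. It does not remove the point, because after exit the investigator usually learns of a pregnancy from the patient.

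A reader might also infer from 5.5.1, which speaks of pregnancies reported during the study, that one notified after exit would not be followed to outcome. Section 5.4.3.1 already requires monitoring to the end of the pregnancy, with no limit to in-study reports. A change to 5.5.1 would therefore be for consistency only.

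Three further arguments have weight:
- The gravest outcomes have their own rules. The birth-defect clause in 5.6 has no time limit and no relatedness condition.
- A patient dosed shortly before closeout is the one most likely to have depleted B cells, and so to be kept in extended follow-up. She can still leave early, for instance on starting azathioprine after closeout.
- A patient who has withdrawn or been lost may not respond to a longer request, so the fix will recover only some of these pregnancies.

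It can also be said that contraception advice is precautionary and that nothing requires a reporting window to match it. That is true, and it makes this a matter of good design rather than a breach of a rule. But the only period for which the protocol signals concern after treatment is 12 months, and it gives no reason for 90 days.

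**Conclusion.** The point holds in a narrow form. A female patient who leaves the study less than 12 months after her last dose is not asked to notify a pregnancy for up to 275 days of the period in which she is advised to avoid one. What can be lost is mainly pregnancies the investigator never hears of.

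There is no gap for induction-only patients who complete Month 18, for patients withdrawn from study drug only who stay to closeout, or for as long as extended follow-up lasts. No analysis is affected.

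The size rests on three assumptions: 12 months is 365 days and applies in full, the *or* in 5.4.3.1 means the later date, and the exit occurs early enough. The documents give no count of patients on any exit route. With planned enrolment of at least 25 patients of both sexes from age 2, the number is likely small. SAP shell DS002SP lists transfer to adult services among its reasons. A reader might take this as evidence that adolescents did leave early, but the shell concerns treatment discontinuation and gives neither sex nor timing.

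A reader might also see a conflict between the entry criterion in 4.1.1, which asks for contraception during participation, and the 12 months in 5.2.3.9. There is none, because following the longer instruction satisfies both.

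**What to change.** In 5.4.3.1 and the consent form, have female patients inform the investigator of a pregnancy *during the study or within 12 months after the last rituximab dose, including retreatment, whichever is later*. The gap then becomes 365 - 365 = 0 for every time of exit, and the ambiguity of the bare *or* is removed. Widening 5.5.1 to pregnancies notified after exit within that window is optional and for consistency only.

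The cost is a protocol amendment with ethics and, where required, regulatory approval (9.5) across the eight countries named in 3.1.1, and revised consent wording with re-consent of current participants (8.2). A few extra pregnancy reports would come in on the existing form. No visits are added, since the 90-day rule already relies on the patient contacting the investigator. The change is worth making, though its practical reach is low.

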5.4.3.2 Pregnancies in Female Partners of Male Patients

Male patients will be instructed through the Informed Consent Form to immediately inform the investigator if their partner becomes pregnant during the study or within 90 days after the last dose of study drug. A Pregnancy Report eCRF should be completed by the investigator within 24 hours after learning of the pregnancy and submitted via the EDC system. Attempts should be made to collect and report details of the course and outcome of any pregnancy in the partner of a male patient exposed to study drug. The pregnant partner will need to sign an Authorization for Use and Disclosure of Pregnancy Health Information to allow for follow-up on her pregnancy. Once the authorization has been signed, the investigator will update the Pregnancy Report eCRF with additional information on the course and outcome of the pregnancy. An investigator who is contacted by the male patient or his pregnant partner may provide information on the risks of the pregnancy and the possible effects on the fetus, to support an informed decision in cooperation with the treating physician and/or obstetrician.

In the event that the EDC system is unavailable, follow reporting instructions provided in Section [5.4.3.1](#).

5.4.3.3 Abortions

Any spontaneous abortion should be classified as an SAE (as the Sponsor considers spontaneous abortions to be medically significant events), recorded on the Adverse Event eCRF, and reported to the Sponsor within 24 hours after learning of the event (see Section [5.4.2](#)).

5.4.3.4 Congenital Anomalies/Birth Defects

Any congenital anomaly/birth defect in a child born to a female patient or female partner of a male patient exposed to study drug should be classified as an SAE, recorded on the Adverse Event eCRF, and reported to the Sponsor within 24 hours after learning of the event (see Section [5.4.2](#)).

5.5 FOLLOW-UP OF PATIENTS AFTER ADVERSE EVENTS

5.5.1 Investigator Follow-Up

The investigator should follow each AE until the event has resolved to baseline grade or better, the event is assessed as stable by the investigator, the patient is lost to follow-up, or the patient withdraws consent. Every effort should be made to follow all SAEs considered to be related to study drug or trial-related procedures until a final outcome can be reported.

During the study period, resolution of AEs (with dates) should be documented on the Adverse Event eCRF and in the patient's medical record to facilitate source data verification. If, after follow-up, return to baseline status or stabilization cannot be established, an explanation should be recorded on the Adverse Event eCRF.

All pregnancies reported during the study should be followed until pregnancy outcome. If the EDC system is not available at the time of pregnancy outcome, follow reporting instructions provided in Section 5.4.3.1.

5.5.2 Sponsor Follow-Up

For SAEs, non-serious AEs of special interest, and pregnancies, the Sponsor or a designee may follow-up by telephone, fax, electronic mail, and/or a monitoring visit to obtain additional case details and outcome information (e.g., from hospital discharge summaries, consultant reports, autopsy reports) in order to perform an independent medical assessment of the reported case.

5.6 POST-STUDY ADVERSE EVENTS

At the study completion/early termination visit, the investigator should instruct each patient to report to the investigator any subsequent AEs that the patient's personal physician believes could be related to prior study drug treatment or study procedures.

The investigator should notify the Sponsor of any death, SAE, or other AE of concern occurring at any time after a patient has discontinued study participation if the event is believed to be related to prior study drug treatment or study procedures. The Sponsor should also be notified if the investigator becomes aware of the development of cancer or a congenital anomaly/birth defect in a subsequently conceived offspring of a patient that participated in this study.

The investigator should report these events to Roche Safety Risk Management on the Adverse Event eCRF. If the Adverse Event eCRF is no longer available, the investigator should report the event directly to Roche Safety Risk Management by telephone (see "Protocol Administrative and Contact Information & List of Investigators").

5.7 EXPEDITED REPORTING TO HEALTH AUTHORITIES, INVESTIGATORS, INSTITUTIONAL REVIEW BOARDS, AND ETHICS COMMITTEES

To determine reporting requirements for single AE cases, the Sponsor will assess the expectedness of these events using the following reference documents:

- Rituximab Investigator's Brochure
- Local prescribing information for rituximab
- Rituximab Core Data Sheet

The Sponsor will compare the severity of each event and the cumulative event frequency reported for the study with the severity and frequency reported in the applicable reference document.

Reporting requirements will also be based on the investigator's assessment of causality and seriousness, with allowance for upgrading by the Sponsor as needed.

6. STATISTICAL CONSIDERATIONS AND ANALYSIS PLAN

This is an exploratory, open-label, single-arm study, with the primary objective of evaluating safety and PK of rituximab in pediatric patients with GPA or MPA. Therefore, there will be no formal statistical hypothesis testing. An analysis will be conducted when the last patient enrolled reaches 6 months. Full details of all planned tables, listings, graphs, and descriptive analyses will be provided in a Statistical Analysis Plan, which will be finalized prior to this analysis. An outline of the proposed analyses is provided herein.

6.1 DETERMINATION OF SAMPLE SIZE

The planned sample size of 25 patients was determined on the basis of the epidemiology of pediatric AAV and information from existing patient cohorts. This sample size takes into the account the number of pediatric patients that would be eligible for treatment with rituximab and that could be expected to be enrolled within a reasonable timeframe. The primary objective of this study is to evaluate the safety and pharmacokinetics of rituximab in these patients. The planned sample size would be sufficient to provide a reasonable estimate of variability for the mean PK parameters based on the observed intra-patient variability from the RAVE study. It would also ensure 95% probability of observing at least one AE when the underlying incidence of that event is $\geq 11\%$.

Given the exploratory nature of this study, there will be no formal statistical hypothesis testing. The study will focus on exploratory estimation of the efficacy and PD endpoints. The planned sample size of 25 would allow estimation of the percentage of patients in remission at 6 months to within 20% of the point estimate (the distance from the point estimate to the upper or lower limit of a 95% CI).

6.2 ANALYSIS POPULATIONS

Safety Analysis Population

All patients who received at least part of one infusion of rituximab will be included in the safety population. Patients will be assigned to a single rituximab treatment group. Safety and efficacy analyses will be based on the safety population.

PK Analysis Population

The PK analysis population will include all patients in the safety population who provide at least one evaluable PK sample.

6.3 SUMMARIES OF CONDUCT OF STUDY

Any eligibility violations or major protocol deviations from the study will be summarized.

6.4 DEMOGRAPHICS AND BASELINE CHARACTERISTICS

Patient demographics and baseline characteristics will be listed and summarized for the safety population.

6.5 PATIENT DISPOSITION AND TREATMENTS

The following data will be listed and summarized for the safety population:

- Patients who completed four IV infusions of rituximab study treatment
- Patients withdrawn prematurely from rituximab study treatment
- Cumulative exposure to rituximab study treatment
- Patients who switched to local standard care
- Details about non-study AAV treatments given over time
- Concomitant medications received
- Patients withdrawn prematurely from study follow-up

